7.1.7.2. Summaries of Non-TEAEs

A brief, high-level summary will be provided for non-TEAEs.

- Non-TEAEs
- Non-TEAEs with Grade 3 or higher
- Non-TE SAEs

Multiple events will be counted only once per participant in each summary. Adverse events will be summarized and listed first in alphabetic order of SOC, and then by PT in descending order of total frequency within each SOC.

7.1.7.3. Summaries of AEs Through FU Week 24

A brief, high-level summary will be provided for AEs through FU Week 24.

In addition, AEs through FU Week 24 for the following summaries will be provided:

- AEs through FU Week 24
- AEs with Grade 3 or higher through FU Week 24
- SAEs through FU Week 24

Multiple events will be counted only once per participant in each summary. Adverse events will be summarized and listed first in alphabetic order of SOC, and then by PT in descending order of total frequency within each SOC.

7.1.7.4. Listings of AEs and Deaths

Data listings will be provided for the following:

- All AEs
- All Non-TEAEs
- All AEs with Grade 3 or higher
- All SAEs
- All Deaths
- All AEs leading to premature discontinuation of any study drug
- All AEs leading to temporary interruption of any study drug

7.1.8. Additional Analysis of Adverse Events – Potential irAEs

Potential irAEs will be analyzed based on a broad (all PTs) search from MedDRA SMQs of Hypersensitivity and Immune-mediated/Autoimmune Disorders.

The number and percentage of participants who experienced any of the above events will be summarized by PT and treatment group for 1) TE potential irAE events, 1) non-TE potential irAE events, and 3) potential irAE events through FU Week 24.

A by-participant listing of identified potential events will be provided.

7.1.9. Additional Analysis of Adverse Events – Potential Uveitis

A predefined MedDRA Search Terms (MST) list consisting of ocular PTs reviewed by an external ophthalmologist and maintained by Patient Safety through MedDRA upversioning for safety monitoring of uveitis in clinical trials will be used for this analysis.

The number and percentage of participants who experienced potential uveitis will be summarized by PT and cohort, and by treatment group within Cohort 2 for 1) TE potential uveitis events, 2) non-TE potential uveitis events, and 3) potential uveitis events through FU Week 24.

A by-participant listing of identified potential events will be provided.

The analysis for potential uveitis will be performed for Final Analysis only.

7.2. Laboratory Evaluations

Laboratory data collected during the study will be analyzed and summarized using both quantitative and qualitative methods. The analysis will be based on values reported in conventional units. When values are below the LOQ, they will be listed as such, and the closest imputed value will be used for the purpose of calculating summary statistics as specified in Section 3.7.

A by-participant listing for laboratory test results will be provided by cohort (and treatment group for Cohort 2), participant ID number and visit in chronological order. Values falling outside of the relevant reference range and/or having a severity grade of 1 or higher on the Gilead Grading Scale for Severity of Adverse Events and Laboratory Abnormalities Version April 1, 2015 (or CTCAE Version 5.0 severity grade for infusion-related AEs) will be flagged in the data listings, as appropriate.

No formal statistical testing is planned.

7.2.1. Summaries of Numeric Laboratory Results

Descriptive statistics (n, mean, SD, median, Q1, Q3, minimum, and maximum) will be provided for each cohort (and for each treatment group for Cohort 2) for chemistry (including alanine aminotransferase [ALT], aspartate aminotransferase [AST], total bilirubin, alkaline phosphatase [ALP], creatine kinase [CK], fasting total cholesterol, fasting glucose, international normalized ratio [INR], lactate dehydrogenase [LDH]), creatinine, and eGFR_{CG} as follows:

- Baseline values
- Values at each postbaseline visit
- Change from baseline at each postbaseline visit

A baseline laboratory value will be defined as the last measurement obtained on or prior to the date of first dose of any study drug. Change from baseline to a postbaseline visit will be defined as the visit value minus the baseline value. The mean, median, Q1, Q3, minimum, and maximum values will be displayed to the reported number of digits; SD values will be displayed to the reported number of digits plus 1.

Median (Q1, Q3) of the observed values for ALT will be plotted using a line plot by treatment group and visit.

In the case of multiple values in an analysis window, data will be selected for analysis as described in Section 3.8.3.

7.2.2. Graded Laboratory Values

The Gilead Grading Scale for Severity of Adverse Events and Laboratory Abnormalities Version April 1, 2015, will be used to assign toxicity grades to laboratory results for analysis. Grade 0 includes all values that do not meet the criteria for an abnormality of at least Grade 1. For laboratory tests with criteria for both increased and decreased levels, analyses for each direction (ie, increased, decreased) will be presented separately.

7.2.2.1. Treatment-Emergent (TE) Laboratory Abnormalities

TE laboratory abnormalities are defined as values that increase at least 1 toxicity grade from baseline at any postbaseline time point, up to and including the composite last on-treatment date plus 30 days. If the relevant baseline laboratory value is missing, any abnormality of at least Grade 1 observed within the time frame specified above will be considered treatment emergent.

7.2.2.2. Non-TE Laboratory Abnormalities

Non-TE laboratory abnormalities are defined as values that increase at least 1 toxicity grade from the last TE laboratory abnormality after the composite last on-treatment date plus 30 days. If the relevant TE laboratory abnormality for a participant is missing, any abnormality of at least Grade 1 observed after the composite last on-treatment date plus 30 days until the end of the study will be consider as non-TE.

7.2.2.3. Laboratory Abnormalities Through FU Week 24

Laboratory abnormalities through FU Week 24 are defined as values that increase at least 1 toxicity grade from baseline at any postbaseline time point, up to and including the composite last on-treatment date plus 24 weeks. If the relevant baseline laboratory value is missing, any abnormality of at least Grade 1 observed within the time frame specified above will be considered as within FU Week 24.

Definitions of the composite last on-treatment date for each cohort can be found in Section 3.8.2.

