3.8.2. Analysis Visit Windows

Participant visits might not occur on protocol-specified days. Therefore, for the purpose of analysis, observations will be assigned to analysis windows as specified in Table 3-1 to Table 3-12.

Data collected up to the last on-treatment date + 3 days will be considered as on-treatment data, whereas data collected afterwards will be considered as follow-up data.

For each drug, the last on-treatment date is defined as follows:

- Last on-treatment date for VIR-2218 = (last injection date of VIR-2218 + 28 days) -1
- Last on-treatment date for nivolumab = (last injection date of nivolumab + 28 days) 1
- Last on-treatment date for selgantolimod = (last dose date of selgantolimod + 7 days) -1

For Cohort 1 and Cohort 2 Group A, the composite last on-treatment date is the latest date of the last on-treatment date of VIR-2218, nivolumab, or SLGN.

For Cohort 2 Group B, the composite last on-treatment date is the latest date of the last on-treatment date of nivolumab or SLGN.

Participants are allowed to continue taking TAF after the discontinuation of study treatments, hence TAF will not be considered for constructing the analysis windows.

The follow-up day (FU Day) in Posttreatment tables is defined as:

• FU Day = Assessment date – composite last on-treatment date.

A baseline value is defined as the last available value collected on or prior to the date of first dose of any study drug. An unscheduled visit prior to the first dosing of study drug will be included in the calculation of the baseline value, if applicable.

The analysis windows for on-treatment assessments are provided in Table 3-1 to Table 3-9. Table 3-10 to Table 3-12 provide analysis windows for posttreatment assessments.

Table 3-1. Cohort 1 and Cohort 2 Group A: Analysis Visit Windows for On-treatment Vital Signs, Hematology, Chemistry, Coagulation, Quantitative Plasma HBV DNA, Quantitative HBV (serum HBsAg, HBcrAg, HBeAg, and HBV RNA), Qualitative HBV Serology (HBeAg, hepatitis B e antibody (HBeAb), HBsAg, and hepatitis B surface antibody (HBsAb))

		Visit Window Study Day	
Visit	Study Day	Lower Limit	Upper Limit
Baseline	1	(none)	1
Week 4	29	2	43
Week 8	57	44	71
Week 12	85	72	92
Week 14	99	93	106
Week 16	113	107	127
Week 20	141	128	155
Week 24	169	156	183
Week 28	197	184	211
Week 32	225	212	239
Week 36	253	240	≥ 253

Table 3-2. Cohort 1 and Cohort 2 Group A: Analysis Visit Windows for On-treatment Urinalysis

		Visit Windo	w Study Day

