Table 3-10. Cohort 1, Cohort 2 Groups A and B: Analysis Visit Windows for Posttreatment Hematology, Chemistry, Coagulation, Quantitative Plasma HBV DNA, HBV genotyping, Quantitative HBV Serology (HBsAg, HBcrAg, HBeAg, and HBV RNA), Qualitative HBV Serology (HBeAg, HBeAb, HBsAg, and HBsAb) and Vital Signs

		Visit Window FU Day	
Visit	FU Day	Lower Limit	Upper Limit
FU Week 2*	15	4	22
FU Week 4	29	23	43
FU Week 8	57	44	71
FU Week 12	85	72	127
FU Week 24	169	128	211
FU Week 36	253	212	295
FU Week 48	337	296	≥ 337

^{*} FU Week 2 was defined in protocol amendment 1, but was removed from protocol amendment 2. Since a substantial amount of participants have already completed FU Week 2 per protocol amendment 1, this visit will be kept in analysis.

Table 3-11. Cohort 2 Groups A and B: Analysis Visit Windows for Posttreatment APRI and FibroTest

		Visit Window FU Day	
Visit	FU Day	Lower Limit	Upper Limit
FU Week 12	85	4	211
FU Week 48	337	212	≥ 337

Table 3-12. Cohort 1, Cohort 2 Groups A and B: Analysis Visit Windows for Posttreatment Body Weight, ECG, Estimated Creatinine Clearance (using the Cockcroft-Gault method)

		Visit Window FU Day	
Visit	FU Day	Lower Limit	Upper Limit
FU Week 48	337	4	≥ 337

3.8.3. Selection of Data in the Event of Multiple Records in an Analysis Visit Window

Depending on the statistical analysis method, single values may be required for each analysis window. For example, change from baseline by visit usually requires a single value, whereas a time-to-event analysis would not require 1 value per analysis window.

If multiple valid, nonmissing, continuous measurements exist in an analysis window, records will be chosen based on the following rules if a single value is needed:

- For baseline, the last nonmissing value on or prior to the first dosing date of study drug will be selected, unless specified differently. If multiple measurements occur on the same day, the last nonmissing value prior to the time of first dosing of study drug will be considered as the baseline value. If there are multiple records with the same time or no time recorded on the same day, the baseline value will be the average of these measurements.
- For postbaseline values (except for alanine aminotransferase [ALT]):
 - The record closest to the nominal day for that visit will be selected.
 - If there are 2 records that are equidistant from the nominal day, the later record will be selected.

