7.1.6.2. Definition of Non-TEAEs

Non-TEAEs are defined as defined as any AEs with an onset date after the composite last on-treatment date + 30 days after permanent discontinuation of study drug through the end of the study.

7.1.6.3. Definition of AEs through FU Week 24

AEs through FU Week 24 are defined as any AEs with an onset date on or after the start date of any study drug and on or before the composite last on-treatment date + 24 weeks after permanent discontinuation of study drug.

Definitions of the composite last on-treatment date for each cohort can be found in Section 3.8.2.

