7.2.2.4. Summaries of Laboratory Abnormalities

Laboratory data that are categorical will be summarized using the number and percentage of participants in the study with the given response at baseline and each scheduled postbaseline visit.

The following summaries (number and percentage of participants) will be provided by lab test and cohort; within cohort 2, the summary will be presented by treatment group (Group A or Group B). Participants will be categorized according to the most severe postbaseline abnormality grade for a given lab test:

- Graded laboratory abnormalities
- Grade 3 or 4 laboratory abnormalities

For all summaries of laboratory abnormalities, the denominator is the number of participants with nonmissing postbaseline values.

The above summaries will be provided for 1) TE laboratory abnormalities, 2) non-TE laboratory abnormalities, and 3) laboratory abnormalities through FU W24.

By-participant listings of all laboratory abnormalities, and Grade 3 or 4 laboratory abnormalities will be provided by cohort, participant ID number and visit in chronological order. The listings will include all test results that were collected throughout the study for the lab test of interest, with all applicable severity grades or abnormal flags displayed.

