7.2.3. Liver-related Laboratory Evaluations

The following liver-related laboratory abnormalities will be summarized using the number and percentage of participants for any postbaseline measurements as follows:

- Confirmed ALT flare: ALT > $2 \times \text{baseline}$ and $\geq 5 \times \text{ULN}$
- Confirmed ALT elevation: $\geq 10 \times \text{ULN}$

- Confirmed ALT elevation with evidence of hepatic toxicity: ALT > 2 × nadir and one of the following confirmed laboratory abnormalities:
 - Total bilirubin $> 2 \times ULN$
 - Elevated INR > 0.5 above baseline and > ULN
 - Abnormal serum ALB > 1 g/dL decrease from baseline

Central Lab ULNs will be used for all liver-related laboratory evaluations.

For individual laboratory tests, participants will be counted once based on the most severe postbaseline values during the analysis period. For the composite criteria of ALT and total bilirubin, INR or ALB, participants will be counted once when the criteria are met at the same postbaseline visit date. The denominator is the number of participants in the Safety Analysis Set who have nonmissing postbaseline values of all relevant tests at the same postbaseline visit date.

ALT flare and confirmed ALT elevations will be summarized by cohort; within Cohort 2, the summary will be presented by treatment group (Group A or Group B).

The above summaries will be provided for 1) TE laboratory abnormalities, 2) non-TE laboratory abnormalities; 3) laboratory abnormalities through FU Week 24.

Listings of participants who met at least 1 of the above criteria for ALT flares and elevations will be provided. For the listings of ALT flares and elevations, AST (U/L), ALB (g/dL), total bilirubin (mg/dL), INR, HBsAg (log₁₀ IU/mL) and HBV DNA (log₁₀ IU/mL) will also be provided.

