Sparse PK for VIR-2218 ⁿ		X			X				X													
Sparse PK for SLGN ⁿ					X				X			X										
Estimated creatinine clearance (using the Cockcroft-Gault method)	X	X			Х								Х	X								Х
Urinalysis	X	X	X	X	X			X	X	X	X	X	X	X								
Urine Drug and Alcohol Screen	X																					
Autoantibodies	X																					
TSH	X									X			X	X								
FSH ^o	X																					
Serum Pregnancy TestP	X													Х								
Urine Pregnancy Test ^p		Х	Х	Х	Х			Х	Х	X	X	X	X			X	Хр	Х	Хр	X	X	Х
Enrollment		X																				
Dispense and Administer TAF as appropriate						7	Tenofo	vir ala	fenam	ide (T	TAF) 2	25-mg t	ablet adminis	stered or	ally da	ly for u	p to 84	weeks				

	Screening	Baseline		,	Treat	ment (Cycles	Wee	ek (± 2	2 days	s) a		EOT (-5 days)				F	ollow-ı	ıp Weel	ks ^b		
	(45 days)	Day 1	4	8	12	13 ^c	14	16	20	24	28	32	36/EOT	EDd	1¢	4	8c	12	16 ^c	24	36	48
Dispense & Administer VIR-2218 SC as appropriate		X	X	X	X			X	X													
Dispense & Administer SLGN9 as appropriate					X	X	Х	Х	X	X	X	X										
Study Drug Accountability			X	X	X		X	X	X	X	X	X	X									

AE = adverse event; APRI = AST to Platelet Ratio Index; CT = computed tomography; ddPCR = digital droplet polymerase chain reaction; ECG = electrocardiogram; ED = early discontinuation; EOT = end of treatment; FSH = follicle-stimulating hormone; FU = follow-up; HBcAg = hepatitis B core-related antigen; HBeAb = hepatitis B e antibody; HBeAg = hepatitis B e antigen; HBv = hepatitis B virus; HCC = hepatocellular carcinoma; HCV = hepatitis C virus; HDV = hepatitis D virus;

IV = intravenous; PBMC = peripheral blood mononuclear cells; PK = pharmacokinetic; SAE = serious adverse event; SC = subcutaneous; SLGN = selgantolimod; TAF = tenofovir alafenamide;

TSH = thyroid-stimulating hormone

- a All study visits except for Weeks 13 and 14.
- b FU Week 1 will have a visit window of + 3 days, FU Weeks 4 through FU Week 16 will have a visit window of ± 5 days, and FU Weeks 24 through FU Week 48 will have a visit window of ± 14 days.
- c Week 13, FU Week 8, and FU Week 16 will be conducted as a virtual/telephonic visit to review AEs, concomitant medications, and overall health of the participant by investigator.
- d The ED visit should be performed within 14 days from notification of study discontinuation. If ED is done in FU period, all of these procedures should be performed.

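### The 'through FU Week 24' laboratory period ends at FU Day 168, one day before the nominal FU Week 24 visit, so on-time and late draws fall outside the tables named for that visit

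*SAP*

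**What the plan says.** SAP Section 7.2.2.3 defines laboratory abnormalities through FU Week 24 as increases of at least one toxicity grade from baseline, "up to and including the composite last on-treatment date plus 24 weeks". Two sets of summaries use this period as their third time slice: graded and Grade 3 or 4 abnormalities in Section 7.2.2.4 ("3) laboratory abnormalities through FU W24"), and confirmed ALT flares and elevations in Section 7.2.3 ("3) laboratory abnormalities through FU Week 24"). Neither section states a cutoff of its own.

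Section 3.8.2 counts follow-up time from the same composite date: "FU Day = Assessment date – composite last on-treatment date". There is no +1 term. Table 3-10, which covers hematology, chemistry and coagulation, gives visit, nominal day, lower limit and upper limit as "FU Week 24 169 128 211".

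The schedules in Appendix 1 state that "FU Weeks 24 through FU Week 48 will have a visit window of ± 14 days".

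For adverse events, Section 7.1.6.3 includes onset dates up to "the composite last on-treatment date + 24 weeks after permanent discontinuation of study drug".

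**The concern.** Both rules count from the composite last on-treatment date, but the period labelled as running through FU Week 24 stops one day short of that visit's nominal day. A draw taken exactly on time, or later within the permitted tolerance, is outside the period.

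The schedules place follow-up laboratory draws at FU Weeks 4, 12 and 24 and then at 36 and 48; the FU Week 8 and 16 visits are virtual. If the FU Week 24 draw is cut off, the last scheduled draw that counts is FU Week 12, nominally FU Day 85. Unscheduled draws up to FU Day 168 still count.

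The error works in one direction. In Section 7.2.2.4 the denominator is participants with nonmissing postbaseline values. A participant with earlier draws stays in the denominator, while a new or worse abnormality at FU Week 24 drops out of the numerator. The reported percentages can therefore be too low, including those for off-treatment ALT flares. The report would also use FU Week 24 in two senses: Section 3.8.3 selects the largest ALT value in the window of FU Days 128 to 211 for the by-visit summaries, so the value shown there as FU Week 24 may be one that the flare table excludes.

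**Working it through.** **Inputs, all from the SAP**
- Laboratory cutoff: composite last on-treatment date + 24 weeks, inclusive (7.2.2.3).
- FU Day = assessment date − composite last on-treatment date (3.8.2).
- FU Week 24: nominal FU Day 169, window 128 to 211 (Table 3-10).
- Visit tolerance at FU Week 24: ±14 days; end-of-treatment (EOT) visit may be up to 5 days early (Appendix 1).
- "Last on-treatment date for selgantolimod = (last dose date of selgantolimod + 7 days) -1", that is, last dose + 6 days (3.8.2).

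**1. Is FU Day 169 a misprint?** No. Every nominal day in Table 3-10 equals 7 × week + 1: 15, 29, 57, 85, 169, 253, 337. The dosing schedule gives the same result.
- Cohort 1 and Cohort 2 Group A: 24 weekly SLGN doses from Day 85 end on 85 + 23 × 7 = Day 246. The composite date is 246 + 6 = Day 252 and Week 36/EOT is Day 253. EOT + 168 days is Day 421, and 421 − 252 = FU Day 169.
- Cohort 2 Group B on the full schedule: the last SLGN dose is 1 + 23 × 7 = Day 162. The composite date is Day 168 and EOT is Day 169. EOT + 168 days is Day 337, and 337 − 168 = FU Day 169.

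**2. The cutoff.** 24 × 7 = 168, so the last included day is FU Day 168. The nominal visit misses it by one day.

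**3. Share of permitted visit days after the cutoff.** The SAP does not state the date from which sites count the ±14 days, so the centre is an assumption:

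| Assumed centre | Permitted FU Days | Days after 168 | Share of 29 |
|---|---|---|---|
| 169 (Table 3-10) | 155 to 183 | 169 to 183 = 15 | 52% |
| 168 | 154 to 182 | 169 to 182 = 14 | 48% |
| 164 (EOT 5 days early: 248 + 168 − 252) | 150 to 178 | 169 to 178 = 10 | 34% |

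These are shares of calendar days, not of participants.

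**4. Share of the analysis window.** The window has 211 − 128 + 1 = 84 days. FU Days 169 to 211 are 43 of them (51%).

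**5. Would a one-day correction do?** No. A cutoff of +169 days admits the exactly on-time visit, but still excludes 14 of 29 tolerance days (170 to 183, centred on 169) and 42 of 84 window days (170 to 211).

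**6. Would FU Day 211 do?** It excludes 0 of 84 window days. It does not bring in the scheduled FU Week 36 draw, whose earliest permitted day is 253 − 14 = FU Day 239.

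**The case against.** The strongest reply is that nothing disappears from the report. Non-treatment-emergent laboratory abnormalities run from the composite date + 30 days to the end of the study and are tabulated for graded abnormalities and for ALT flares and elevations. A graded value at FU Week 24 that exceeds every earlier grade also exceeds the last treatment-emergent abnormality, or there was none, so it counts there. It also enters the FU Week 24 by-visit summaries and the listings. This stands: it would be wrong to infer that the data are lost. But the non-treatment-emergent table does not replace the faulty one, because it uses a different reference grade and runs past FU Week 24.

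A reader might also infer that adverse events reported at an on-time or late FU Week 24 visit are excluded. Section 7.1.6.3 does not support that. It applies to onset date, so an event with earlier onset first reported at the visit is still counted; only onsets from FU Day 169 fall outside. A fixed 24-week onset period is an ordinary definition, and the effect is small.

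A reader might further take 52% as the share of participants affected, or 100% if all visits fall on the nominal day. The first needs visits spread evenly around FU Day 169, and the second is a bounding case. The SAP gives neither the anchor nor the spread. Follow-up timed from an early EOT puts the visit at FU Day 164, inside the cutoff. For participants who stopped early, including Group B, the composite date can be the last nivolumab dose + 27 days; if their follow-up was timed from stopping, the visit could fall well before FU Day 168.

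Finally, the SAP does not say that this period was meant to match the primary analysis time point. That is a reasonable reading of the label, but the inconsistency does not depend on it.

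**Conclusion.** The laboratory cutoff is wrong as written. On the SAP's own definitions, an on-time or late FU Week 24 sample is FU Week 24 data in one set of tables and outside the 'through FU Week 24' period in another, and no other provision repairs this. The consequence is a possible understatement of the numerators in one of three descriptive time slices, for graded laboratory abnormalities and for ALT flares and elevations.

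The number of participants affected cannot be derived from the SAP. Between 10 and 15 of the 29 permitted visit days are excluded when the tolerance is centred anywhere from FU Day 164 to FU Day 169. A participant whose visit falls on or before FU Day 168 is not affected.

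The documents do not support extending the point to the primary endpoint, which does not use this cutoff, or treating the adverse event period as equally faulty.

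**What to change.** In Section 7.2.2.3, replace the fixed 24 weeks with one of two rules:
- all samples assigned to the FU Week 24 analysis window or earlier (FU Day ≤ 211); or
- all samples up to and including the participant's FU Week 24 visit date.

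Section 7.2.3 takes its period from 7.2.2.3, so it needs only a cross-reference.

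For adverse events (7.1.6.3), either keep the fixed 24-week onset period or align it with the FU Week 24 visit date. Do not extend it to FU Day 211: that would place onsets up to about 30 weeks (211 / 7 = 30.1) under a Week 24 label, and at the Primary Analysis some participants may not yet have been observed that long.

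The cost is a wording change and one derivation constant, with no new data. Section 1 of the SAP requires changes after finalization to be documented in the CSR, so record it there.
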